Study Sponsor	Rhizen Pharmaceuticals S.A.
Study Centers	Approximately about 15 study centers
Study Objectives	
Primary Objectives
 
 • To characterize safety, tolerability and to establish the maximum tolerated dose (MTD) of Tenalisib in combination with Romidepsin in patients with R/R T-cell lymphoma. 
Secondary Objectives
 
 • To assess the preliminary anti-tumor activity of various dose levels of Tenalisib in combination with Romidepsin, as determined by the objective response rate (ORR) and Duration of Response (DoR) • To characterize the Pharmacokinetics (PK) of Tenalisib and Romidepsin when given in combination. 
Exploratory Objectives
 
 • To correlate clinical efficacy with markers that include but are not limited to quantitative and qualitative measurements of malignant cells, cytokines, and chemokines in blood/serum.
Endpoints	
Safety:
 
 • Adverse Event (AE), Grade 3/ 4 AEs, Serious and fatal Adverse Event (SAE), graded using NCI CTCAE Version 5.0. 
Efficacy:
 
 • Objective response rate (ORR), defined as sum of CR and PR rates, assessed according to the Lugano Classification for initial evaluation, staging, and response assessment of Hodgkin/non-Hodgkin lymphoma in PTCL patients; and according to the modified Severity Weighted Assessment Tool (mSWAT) in CTCL patients. • Duration of Response (DoR), calculated as time from the initial response to documented disease progression. 
Pharmacokinetics:
 
 • PK Parameters [AUC $(0-\infty)$, AUC $(0-t)$, C_{max}, t_{max}, K_{el}, and $t_{1/2}$] of Tenalisib and Romidepsin.

	
Correlative/Exploratory:
 
 Correlative markers include baseline and on-treatment serum levels of chemokines, cytokines, antibodies to tumor antigens, and other immune mediators (e.g. SIL2R and CTACK for PTCL; CD30, IL-31 and IL-32 for CTCL) as deemed relevant by the sponsor. 																

Study Design and Procedure
	
This is a multi-center, open label, non-randomized, two-part Phase I/II study of Tenalisib in combination with Romidepsin in adult patients with relapsed/refractory TCL. The first part is an open label, 3+3 design, Phase I dose escalation for MTD determination. The second part is a Phase II, dose expansion to delineate the safety and anti-tumor activity of the combination at the MTD/optimal dose.
 
In dose escalation, a minimum of 2 and maximum 18 patients will be enrolled in three dose levels unless additional dose levels are required to reach MTD/optimal dose. In dose expansion, up to 24 TCL patients will be enrolled (Group 1 = 12 PTCL patients and Group 2 = 12 CTCL patients).
 
The study will end when all ongoing subjects have reached their third tumor assessment on Cycle 8/Day 1 (C8D1) or have discontinued from the study for any reason, whichever is earlier. At the end of the study, all ongoing patients with no evident disease progression will be given the opportunity to enroll in an open-label compassionate use study protocol and will be followed up.
 
PHASE I (DOSE ESCALATION):
 
Sequential dose escalation will begin with Cohort 1. A minimum of three patients will be enrolled at each dose level. Dose levels will be increased in successive increments according to the dose escalation cohorts mentioned in the table below. Escalation to the next cohort will occur if no patient within a three-patient cohort or one in six patients experiences a dose limiting toxicity (DLT). De-escalation to different lower doses in case DLT criteria is met, will be done as per the discretion of Safety Review Committee (SRC). The highest doses of the combination (Tenalisib at 800 mg BID plus Romidepsin IV 14 mg/m²) will be considered as optimal in case there is no DLT at this dose level.
 
Dose escalation scheme:
 
  
 Cohort	N	Tenalisib¹	Romidepsin²	
   
 Cohort 1	3-6	Tab. 400 mg PO twice a day	IV 12 mg/m² on Day 1, 8 and 15	
 
 Cohort 2	3-6	Tab. 600 mg PO twice a day	IV 12 mg/m² on Day 1, 8 and 15	
 
 Cohort 3	3-6	Tab. 800 mg PO twice a day	IV 14 mg/m² on Day 1, 8 and 15	
  
 
Note: Alternate dose levels/dosing schedules may be considered by the SRC if deemed essential based on emerging safety and PK data.
 
¹In case the dose (e.g. 800 mg BID) is leading to DLT of the combination, the dose of Tenalisib will be reduced to lower dose (e.g. 600 mg BID) and will be evaluated for safety in a separate cohort.
	Cohort	N	Tenalisib ¹	Romidepsin ²	Cohort 1	3-6	Tab. 400 mg PO twice a day	IV 12 mg/m ² on Day 1, 8 and 15	Cohort 2	3-6	Tab. 600 mg PO twice a day	IV 12 mg/m ² on Day 1, 8 and 15	Cohort 3	3-6	Tab. 800 mg PO twice a day	IV 14 mg/m ² on Day 1, 8 and 15
Cohort	N	Tenalisib ¹	Romidepsin ²														
Cohort 1	3-6	Tab. 400 mg PO twice a day	IV 12 mg/m ² on Day 1, 8 and 15														
Cohort 2	3-6	Tab. 600 mg PO twice a day	IV 12 mg/m ² on Day 1, 8 and 15														
Cohort 3	3-6	Tab. 800 mg PO twice a day	IV 14 mg/m ² on Day 1, 8 and 15														

	
²In case the dose (e.g. 14 mg/m²) is leading to DLT of the combination, the dose of Romidepsin will be reduced to lower dose (e.g. 12 mg/m²) and if required further to 10 mg/m² and will be evaluated for safety in a separate cohort.
 
DLT assessment: The data of at least 3 patients will be required for DLT assessment. DLT assessment period will be 28-days (inclusive) (will begin on C1D1 and end on C2D1), unless extended by the medical monitor. In the first cycle, patients must have been treated with at least 2 doses of Romidepsin and minimum 14 days with Tenalisib to be considered eligible for safety analysis unless identified to have a DLT. Patients who experience a DLT will be considered evaluable regardless of the number of doses received.
 
Individual patients will be considered for Intra-subject dose escalation at the discretion of investigator after discussion with medical monitor.
 
PHASE II (DOSE EXPANSION): After establishing the MTD/optimal dose, the Phase II (expansion part) will be opened as approved by the SRC to enroll two groups of patients.
 
  
 Group	N	Patient population	Tenalisib	Romidepsin	
   
 Group 1	12	Patients with R/R PTCL	MTD/Optimal dose	MTD/Optimal dose on Day 1, 8 and 15	
 
 Group 2	12	Patients with R/R CTCL	MTD/Optimal dose	MTD/Optimal dose on Day 1, 8 and 15	
  
 
The details of the study procedures are given in the schedule of events.
	Group	N	Patient population	Tenalisib	Romidepsin	Group 1	12	Patients with R/R PTCL	MTD/Optimal dose	MTD/Optimal dose on Day 1, 8 and 15	Group 2	12	Patients with R/R CTCL	MTD/Optimal dose	MTD/Optimal dose on Day 1, 8 and 15
Group	N	Patient population	Tenalisib	Romidepsin												
Group 1	12	Patients with R/R PTCL	MTD/Optimal dose	MTD/Optimal dose on Day 1, 8 and 15												
Group 2	12	Patients with R/R CTCL	MTD/Optimal dose	MTD/Optimal dose on Day 1, 8 and 15												
No. of Patients	
Phase I: Total 2-18 patients will be enrolled in 3 escalating cohorts unless additional dose levels are required to reach MTD/ optimal dose.
 
Phase II: Total 24 patients with relapsed/refractory TCL will be enrolled.
															
Inclusion Criteria	
Inclusion criteria
 
 1. Age \geq18 years on the day of signing informed consent. 2. Pathologically confirmed T-cell lymphoma at the enrolling institution*. 3. Disease status as defined as relapsed after or refractory to at least one systemic therapy. 4. The patients should have received NOT more than three prior systemic combination chemotherapies. 5. Must have ECOG performance status \leq 2 6. PTCL patients must have measurable disease defined as at least one bi-dimensional measurable lesion with minimum measurement of > 1.5 cm in the longest diameter. 7. Life expectancy of at least 3 months 8. Toxicities related to prior therapy must have returned to Grade 1 or less, except for alopecia. 															

	
9. Adequate bone marrow, liver and renal function in line with below mentioned laboratory requirements. Hemoglobin and platelet requirements should not be met by use of recent transfusion or growth factor support (GCSF or erythropoietin) within 3 weeks prior to treatment initiation.
 
 • Hemoglobin ≥ 8.0 g/dL • Absolute neutrophil count (ANC) $\geq 1,000/\mu\text{L}$ • Platelet count $\geq 75,000/\mu\text{L}$ • Total bilirubin ≤ 1.5 times the ULN (or $\leq 3 \times$ ULN, if patient has Gilbert syndrome) • AST (SGOT) and ALT (SGPT) $\leq 3 \times$ ULN; ≤ 5 ULN in case of liver involvement • Calculated creatinine clearance (CrCl) > 50 ml/min by Cockcroft-Gault formula. 
10. Use of an effective means of contraception for women of childbearing potential and men with partners of childbearing potential.
 
11. Female subject of childbearing potential should have a negative urine or serum pregnancy within 72 hours prior to receiving the first dose of study medication. If the urine test is positive or cannot be confirmed as negative, a serum pregnancy test will be required.
 
12. Provide written informed consent prior to any study-specific screening procedures.
 
13. Willingness and capability to comply with the requirements of the study.
 
*Note: The EORTC classification of CTCLs will be used to classify patients. CTCL includes other variants other than MF (e.g. Gamma delta cutaneous T-cell lymphoma or subcutaneous or panniculitic like T-cell lymphoma and CD8 positive T-cell lymphoma). PTCL includes patients with predominantly nodal disease (systemic involvement) but some patients (e.g. AITCL or ATCL) may have skin lesions. Patient having both skin and node lesions will be placed into one of the group (CTCL or PTCL) as approved by investigator.

Exclusion Criteria	
 1. Patient receiving anticancer therapy including any investigational therapy (e.g. chemotherapy, biologic therapy, hormonal therapy, radiotherapy (except limited field palliative radiation), surgery and/or tumor embolization) ≤ 3 weeks or 5 half-lives (whichever is shorter) prior to C1D1. 2. Patient who discontinued prior therapy with PI3K inhibitors or HDAC inhibitors due to drug toxicity. 3. PTCL patients with Allo-SCT on active GVHD or immunosuppression therapy within 3 months prior to C1D1. CTCL patients with the history of Allo-SCT will be excluded. 4. Patient with medical conditions requiring the use of systemic immunosuppressive medications (> 20 mg/day of prednisone or equivalent). 5. Severe bacterial, viral or mycotic infection requiring systemic treatment. 6. Pregnancy or lactation. 7. History of chronic liver disease, hepatic veno-occlusive disease, or current alcohol abuse.

	
 8. Known clinically active central nervous system (CNS) or meningeal involvement. (Note: In the absence of symptoms, investigation into CNS involvement is not required. Patients are eligible if metastases have been treated and patients are neurologically returned to baseline or neurologically stable for at least 4 weeks prior to C1D1). 9. Known seropositive requiring anti-viral therapy for human immunodeficiency virus (HIV) infection. 10. Known seropositive requiring anti-viral therapy for hepatitis B virus (HBV) infection OR evidence of active hepatitis B infection as defined by detectable viral load if the antibody tests are positive. [Note: A positive HBcAb subject with an undetectable/negative hepatitis B DNA test (e.g., polymerase chain reaction [PCR] test) can be enrolled]. 11. Known seropositive requiring anti-viral therapy for hepatitis c virus (HCV) infection OR patients with positive hepatitis C virus Ab. 12. Subjects with active EBV unrelated to underlying lymphoma (positive serology for anti-EBV VCA IgM antibody and negative for anti-EBV EBNA IgG antibody, or clinical manifestations and positive EBV PCR consistent with active EBV infection). 13. Subject with active CMV (positive serology for anti-CMV IgM antibody and negative for anti-CMV IgG antibody and positive CMV PCR with clinical manifestations consistent with active CMV infection) and requiring therapy. [Note: Carriers will be monitored per institutional guidelines.] 14. Subjects with concomitant second malignancies (except adequately treated non-melanomatous skin cancers, ductal carcinoma in situ, superficial bladder cancer, prostate cancer or in situ cervical cancers) are excluded unless a complete remission is achieved at least 2 years prior to study entry and no additional therapy (except adjuvant or maintenance therapy to reduce the risk of recurrence) is required or anticipated to be required during the study period. 15. Administration of any of the following within 1 week prior to C1D1: 
 • Strong inhibitors or inducers of CYP3A4 including but not limited to grapefruit products, herbal supplements and drugs • Strong inhibitors or inducers of CYP2C9 including but not limited to herbal supplements and drugs • Substrates of CYP3A4 enzyme with a narrow therapeutic range. 16. History of Grade 4 anaphylactic reaction. 17. Administration of live vaccines within 6 weeks of C1D1. 18. History of prior surgery or gastrointestinal dysfunction that may affect drug absorption (e.g., gastric bypass surgery, gastrectomy) 19. Current history of a serious uncontrolled medical disorder, metabolic dysfunction, physical examination findings, or clinical laboratory findings giving reasonable suspicion of a disease or condition that contraindicates use of an investigational drugs or render the subject at high risk from treatment complications.
--	---

	
20. Uncontrolled or significant cardiovascular disease including, but not limited to:
 
 • Congenital long QT syndrome. • QTcF interval > 450 msec • Myocardial infarction or stroke/TIA within the past 6 months • Uncontrolled angina within the past 3 months • Significant ECG abnormalities including 2nd degree atrio- ventricular (AV) block (AV) block type II, 3rd degree AV block. • History of clinically significant arrhythmias (such as ventricular tachycardia, ventricular fibrillation or torsades de pointes), • History of other clinically significant heart disease (ie, cardiomyopathy, congestive heart failure with NYHA functional classification III-IV, pericarditis, significant pericardial effusion) • Requirement for daily supplemental oxygen therapy.
Estimated Study Participation	
Dose Escalation: Approximately 10 months for accrual and follow up Dose Expansion: Approximately 18 months for accrual plus patient follow up.

Assessment of Response	
Initial disease assessment will be performed at screening. The response to treatment will be done at C3D1 (\pm 7 days), C5D1 (\pm 7 days), C8D1 (\pm 7 days) and/ or at the EOT and or as clinically indicated (if clinical progression is suspected or for confirmation of complete response/disease progression). The following assessments will be done.
 
PTCL: The response assessment will be done using CT scan as per the Lugano classification. PET-CT will be preferred for FDG-avid lymphomas. PET-CT will be performed at C3D1 (\pm 7 days) and to confirm the CR. Bone marrow biopsy will be performed to confirm complete response.
 
CTCL: Response assessment in CTCL will be done as per the modified Severity Weighted Assessment Tool (mSWAT). Additionally, CT scan will be done in the CTCL patients with lymph node and visceral involvement. CTCL patients with subcutaneous lesions which cannot be measured by mSWAT will be assessed by change in PET-CT avid lesions. Bone marrow biopsy will be performed in patients with B₂ blood involvement. In these patients, Sezary cell count will be quantified by flow cytometry or morphology in blood/bone marrow.

Study Treatment	
For purposes of this study, each cycle of therapy consists of 4 weeks.
 
Tenalisib: Tenalisib will be administered from Day 1-28 in 28-days of cycle up to C8D1 in absence of disease progression and unacceptable toxicity. However, in Cycle 1 of Dose Escalation, Tenalisib will be started from Day 3 to permit pharmacokinetic analysis of Romidepsin alone prior to combination treatment.

	
Tenalisib tablets will be self-administered orally twice daily one hour before a major meal (e.g. breakfast and dinner). Patients should not consume food during this one-hour period. On the day of Romidepsin therapy, the morning dose of Tenalisib will be given in clinic one hour prior to Romidepsin infusion.
 
Romidepsin: Romidepsin will be administered intravenously (IV) over a 4-hour period on days 1, 8 and 15 in a 28-day cycle.

Statistical Analysis	
Part 1: In Dose Escalation, three patients per cohort are considered appropriate for the assessment of overall safety and tolerability and for providing adequate confidence for dose escalation. No formal sample size and power analysis is done. Accordingly, total 2-18 patients will be enrolled in 3 escalating cohorts unless additional dose levels are required to reach MTD/ optimal dose. Optimal dose will be determined by the SRC.
 
Part 2: Total 24 patients with relapsed/refractory TCL will be enrolled in two groups (12 patients in each group).
 
The SRC may modify the sample size due to unforeseen clinical situations.

GENERAL INFORMATION	
SPONSOR	[REDACTED]
PRINCIPAL INVESTIGATOR AND STUDY CHAIR	[REDACTED]
CO- PRINCIPAL INVESTIGATOR	[REDACTED]
SPONSOR'S REPRESENTATIVE	[REDACTED]
SPONSOR'S MEDICAL EXPERT	[REDACTED]
STATISTICIAN	[REDACTED]
CLINICAL PK, BIOMARKER LABORATORY	[REDACTED]

List of Abbreviations

AE	Adverse Event
ALP	Alkaline Phosphatase
ALT (SGOT)	Alanine aminotransferase
ANC	Absolute Neutrophil Count
aPTT	Activated Partial Thromboplastin Time
Allo-SCT	Allogeneic Hematopoietic Stem Cell Transplantation
AST (SGPT)	Aspartate aminotransferase
AUC _{0-t}	Area Under the plasma-concentration time curve from zero up to the last measurable concentration
BID	Twice Daily
β-HCG	β-human chorionic gonadotropin
BSA	Body Surface Area
C _{max}	Peak Drug Concentration
CBC	Complete Blood Count
CMV	Cytomegalovirus
CNS	Central Nervous System
CR	Complete Response
CrCl	Creatinine Clearance
CT	Computed Tomography
CTCAE	Common Terminology Criteria for Adverse Events
CTCL	Cutaneous T cell Lymphoma
DLT	Dose Limiting Toxicity
DoR	Duration of Response
ECG	Electrocardiogram
eCRF	Electronic Case Report Form
ECOG PS	Eastern Cooperative Oncology Group Performance Status
EORTC	European Organization for Research and Treatment of Cancer
EOS	End of Study
EOT	End of Treatment
FDA	Food and Drug Administration
FSH	Follicular Stimulating Hormone
GCP	Good Clinical Practices
GGT	Gamma Glutamyl Transpeptidase
G-CSF	Granulocyte Colony-Stimulating Factor
GVHD	Graft Versus Host Disease
Hb	Hemoglobin
HBV	Hepatitis B Virus
HCV	Hepatitis C Virus
HDL	High-Density Lipoprotein
HDPE	High-density Polyethylene
HEENT	Head, Eyes, Ears, Nose and Throat
HIPAA	Health Insurance Portability and Accountability Act
HIV	Human Immune Deficiency Virus
HPV	Human Papilloma Virus
IB	Investigator's brochure

ICF	Informed Consent Form
ICH	International Conference on Harmonization
IEC	Independent ethics committee
INR	International Normalized Ratio
IRB/IEC	Institutional Review Board/Independent Ethics Committee
IRR	Infusion related reactions
ISCL	International Society of Cutaneous Lymphoma
IUD	Intrauterine Device
IUS	Intrauterine System
Kel	Elimination Constant
LDH	Lactate Dehydrogenase
LDL	Low-Density Lipoprotein
LLN	Lower Limit of Normal
LMWH	Low Molecular Weight Heparin
MedDRA	Medical Dictionary for Regulatory Activities
MF	Mycosis fungoides
mITT	Modified Intent-to-Treat
MRI	Magnetic Resonance Imaging
MTD	Maximum Tolerated Dose
mSWAT	Modified Severity Weighted Assessment tool
NCI	National Cancer Institute
NOAEL	No-Observed-Adverse Effect Level
NSAID	Non-Steroidal Anti-Inflammatory Drug
NYHA	New York Heart Association
ORR	Objective Response Rate
pAKT	Phospho AKT
PCP	Pneumocystis Carinii
PD	Progressive Disease
PD-1	Programmed Death-1
PET	Positron Emission Tomography
PFS	Progression-Free Survival
PI	Principle Investigator
PI3K	Phosphoinositide-3-Kinase
PK	Pharmacokinetics
PP	Per-Protocol
PR	Partial Response
PTCL	Peripheral T-Cell Lymphoma
QA	Quality Assurance
QTcF	Frederica's (QTcf)
SAE	Serious Adverse Events
SAP	Statistical Analysis Plan
SAS	Statistical Analysis Software
SD	Stable Disease
SDV	Source Document Verification
SLL	Small Lymphocytic Lymphoma
SOP	Standard Operating Procedures
SRC	Safety Review Committee
SS	Sezary Syndrome

SUV	Standardized Uptake Value
$t_{1/2}$	Plasma Half Life
t_{max}	Time to maximum plasma concentration
TAM	Tumor Associated Macrophages
TEAE	Treatment-Emergent Adverse Event
TG	Triglyceride
TIA	Transient Ischemic Attack
TID	Thrice Daily

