4.2 Exclusion Criteria

1. Patient receiving anticancer therapy including any investigational therapy (e.g. chemotherapy, biologic therapy, hormonal therapy, surgery, radiotherapy (except limited field palliative radiation) and/or tumor embolization) ≤ 3 weeks or 5 half-lives (whichever is shorter) prior to C1D1.
2. Patient who discontinued prior therapy with PI3K inhibitors or HDAC inhibitors due to drug toxicity.
3. PTCL patients with Allo-SCT on active GVHD or immunosuppression therapy within 3 months prior to C1D1. CTCL patients with the history of Allo-SCT will be excluded.
4. Patient with any medical conditions requiring the use of systemic immunosuppressive medications (> 20 mg/day of prednisone or equivalent).

5. Severe bacterial, viral or mycotic infection requiring systemic treatment.
6. Pregnancy or lactation.
7. History of chronic liver disease, hepatic veno-occlusive disease, or current alcohol abuse.
8. Known clinically active central nervous system (CNS) or meningeal involvement. (Note: In the absence of symptoms, investigation into CNS involvement is not required. Patients are eligible if metastases have been treated and patients are neurologically returned to baseline or neurologically stable for at least 4 weeks prior to C1D1).
9. Known seropositive requiring anti-viral therapy for human immunodeficiency virus **(HIV) infection.**
10. Known seropositive requiring anti-viral therapy for hepatitis B virus (HBV) infection **OR** evidence of **active hepatitis B infection** as defined by detectable viral load if the antibody tests are positive. [Note: A positive HBcAb subject with an undetectable/negative hepatitis B DNA test (e.g., polymerase chain reaction [PCR] test) can be enrolled]
11. Known seropositive requiring anti-viral therapy for hepatitis c virus (HCV) infection **OR** patients with positive hepatitis C virus Ab.
12. Subjects with active EBV unrelated to underlying lymphoma (positive serology for anti-EBV VCA IgM antibody and negative for anti-EBV EBNA IgG antibody), or clinical manifestations and positive EBV PCR consistent with active EBV infection.
13. Subject with active CMV (positive serology for anti-CMV IgM antibody and negative for anti-CMV IgG antibody and positive CMV PCR with clinical manifestations consistent with active CMV infection) and requiring therapy. [Note: Carriers will be monitored per institutional guidelines.]

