6.7 Radiological Evaluations

Initial disease assessment by tumor imaging (baseline scan) must be performed within 28 days prior to C1D1. The site investigator/designee must review radiological images to confirm the subject has measurable disease as defined in the inclusion criteria. Disease assessments or scans performed as part of routine clinical management are acceptable for use as the screening scan if they are of diagnostic quality and performed within 28 days prior to the first dose of trial treatment.

- **PTCL and CTCL patients with lymph node/visceral involvement:**

Computed tomography (CT) scan (chest/abdomen/pelvis/neck as appropriate) will be performed at screening for disease assessment. PET-CT is preferred for FDG-avid lymphomas. Other radiological evaluations (e.g. X-ray/MRI/USG) will be performed if warranted.

- **CTCL patients with skin and blood involvement:**

CT scan will be performed at screening for disease assessment.

- In patients with clinically early disease (maximum/current $T_{1-2}N_0M_0B_{0-1}$), repeat scans should not be performed except in cases of an objective response (OR) in the skin.
- In those patients with more advanced disease at baseline ($TNMB > T_{1-2}N_0M_0B_{0-1}$), CT scan should be performed at the time of PR and CR in the skin; any time there is a question of new or PD in the lymph nodes or viscera; and at end of study.

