8 ASSESSMENT OF EFFICACY

8.1 Specification of the Efficacy Parameters

Evaluable for objective response: Patients who have had a pre-treatment baseline efficacy evaluation and at least one post-treatment efficacy evaluation will be considered evaluable for response. “**Investigator assessed response**” will be used in the study. These patients will have their response classified according to the definitions stated below.

Disease parameters:

- **Measurable disease:** Measurable lesions are defined as those that can be accurately measured in at least two dimensions with conventional techniques (PET/CT, MRI, x-ray) or as $>1.5 \text{ cm}$ with spiral CT scan. All tumor measurements should be recorded in centimeters.
- **Non-measurable disease (evaluable disease):** All other lesions (or sites of disease) including small lesions, ($<1 \text{ cm}$ using spiral CT scan) are considered non-measurable disease. Bone lesions, leptomeningeal disease, ascites, pleural/pericardial effusions, lymphangitis, and cystic lesions are all non-measurable.
- **Target lesions:** All measurable lesions up to a maximum of 6 lesions total, representative of all involved organs, should be identified as target lesions and recorded and measured at baseline.

Target lesions should be selected on the basis of their size (lesions with the longest SPD diameter), and the highest SUV avidity (high SUV lesions may be prioritized even if not the largest lesions, and their suitability for accurate repeated measurements (either by imaging techniques or clinically). A baseline sum of the diameters (longest for non-nodal lesions, short axis for nodal lesions) for all target lesions will be calculated and reported as the baseline sum diameters. The baseline sum of the diameters will be used as reference to further characterize any objective tumor regression in the measurable dimension of the disease.

- **Non-target lesions:** All other lesions (or sites of disease) including any measurable lesions over and above the 6 target lesions should be identified as non-target lesions and should also be recorded at baseline. Measurements of these lesions are not required, but the presence, absence, or in rare cases unequivocal progression of each should be noted throughout follow-up.

Evaluation of best objective response: The best objective response is the best response recorded from the start of the treatment until disease progression/recurrence.

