Appendix B: Contraceptive Guidelines and Pregnancy

Women Not of Childbearing Potential are defined as Follows
Women are considered post-menopausal and not of child bearing potential if they have had 12 months of natural (spontaneous) amenorrhea with an appropriate clinical profile (e.g. age appropriate, history of vasomotor symptoms) or six months of spontaneous amenorrhea with serum FSH levels > 40 mIU/mL] or have had surgical bilateral oophorectomy (with or without hysterectomy) at least six weeks ago. In the case of oophorectomy alone, only when the reproductive status of the woman has been confirmed by follow up hormone level assessment is she considered not of child bearing potential.
Contraceptive Guidelines for Women of Child-Bearing Potential
Women of child-bearing potential, defined as all women physiologically capable of becoming pregnant, must use highly effective contraception during the study and for 5 T1/2 (48 hrs) plus an additional 4 weeks after stopping treatment . The highly effective contraception is defined as either:

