Appendix C: Response Criteria for NHL-The Lugano classification

Response and Site	PET-CT-Based Response	CT-Based Response
COMPLETE	Complete metabolic response	Complete radiologic response (all of the following)
Lymph nodes and extra lymphatic sites	Score 1, 2, or 3* with or without a residual mass on 5PS† It is recognized that in Waldeyer's ring or extra-nodal sites with high physiologic uptake or with activation within spleen or marrow (e.g., with chemotherapy or myeloid colony-stimulating factors), uptake may be greater than normal mediastinum and/or liver. In this circumstance, complete metabolic response may be inferred if uptake at sites of initial involvement is no greater than surrounding normal tissue even if the tissue has high physiologic uptake	Target nodes/nodal masses must regress to ≤ 1.5 cm in LDi No extra lymphatic sites of disease
Nonmeasured lesion	Not applicable	Absent
Organ enlargement	Not applicable	Regress to normal
New lesions	None	None
Bone marrow	No evidence of FDG-avid disease in marrow	Normal by morphology; if indeterminate, IHC negative
PARTIAL	Partial metabolic response	Partial remission (all of the following)
Lymph nodes and extra lymphatic sites	Score 4 or 5† with reduced uptake compared with baseline and residual mass(es) of any size At interim, these findings suggest responding disease At end of treatment, these findings indicate residual disease	$\geq 50\%$ decrease in SPD of up to 6 target measurable nodes and extra-nodal sites When a lesion is too small to measure on CT, assign 5 mm \times 5 mm as the default value When no longer visible, 0 \times 0 mm For a node > 5 mm \times 5 mm, but smaller than normal, use actual measurement for calculation
Nonmeasured lesions	Not applicable	Absent/normal, regressed, but no increase
Organ enlargement	Not applicable	Spleen must have regressed by $> 50\%$ in length beyond normal
New lesions	None	None
Bone marrow	Residual uptake higher than uptake in normal marrow but reduced compared with baseline (diffuse uptake compatible with reactive changes from chemotherapy allowed). If there are persistent focal changes in the marrow in the context of a nodal response, consideration should be given to further evaluation with MRI or biopsy or an interval scan	Not applicable

NO RESPONSE OR STABLE DISEASE	No metabolic response	Stable disease

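### A lesion irradiated between the baseline scan and C1D1 stays a target lesion, so where it dominates the target burden its shrinkage can be scored as a partial response to the combination

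*Protocol*

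**What the plan says.** **Washout.** The synopsis version of exclusion criterion 1 carves out "radiotherapy (except limited field palliative radiation), surgery and/or tumor embolization". Protocol 4.2 keeps the exemption in its own wording: "radiotherapy (except limited field palliative radiation) and/or tumor embolization) ≤ 3 weeks or 5 half-lives (whichever is shorter) prior to C1D1". Neither place gives a minimum interval between the exempt radiation and C1D1.

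**Baseline scan.** Protocol 6.7 states: "Initial disease assessment by tumor imaging (baseline scan) must be performed within 28 days prior to C1D1". It adds: "Disease assessments or scans performed as part of routine clinical management are acceptable for use as the screening scan". Protocol 6.3 also gives 28 days, but 6.4 gives 28 weeks. No section requires the baseline scan or mSWAT to follow the last radiation.

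**Target lesions.** Protocol 8.1: "All measurable lesions up to a maximum of 6 lesions total, representative of all involved organs, should be identified as target lesions". The selection factors are size, SUV avidity and suitability for repeat measurement. Prior irradiation is not mentioned. Inclusion criterion 6 asks PTCL patients for one measurable lesion.

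**Response.** In Appendix C, a CT-based PR requires a 50% or greater "decrease in SPD of up to 6 target measurable nodes and extra-nodal sites". The first scheduled read is at C3D1 (study day 57, ±7 days).

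**Other rules on radiation.** Protocol 5.4 lists it among the anti-lymphoma treatments barred during the trial, without saying when the bar begins. Protocol 6.3.4 records prior radiation as history. The SAP does not use it, either in the mITT definition (7.3) or in the ORR analysis (10.5.1).

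**The concern.** ORR is meant to show the activity of Tenalisib plus Romidepsin. Change from baseline measures that only if no other effective local treatment falls between baseline and the first response read. Here the exemption, the age allowed for the scan and the target rule combine to let one in. Choosing targets by size and avidity does not help, because a bulky, avid node is a natural choice as a target and may also be one that is palliated.

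The expansion groups have 12 patients each, so a single misclassified patient is visible in the result. A false PR also enters the DoR analysis, although the direction of its effect there is not fixed, since progression is judged from nadir.

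**Working it through.** The plan states no figure on this point to reproduce. The check is one of timing and then of SPD arithmetic.

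**1. Is the sequence allowed?** A scan on day −28 satisfies 6.7. Exempt radiation on any day from −27 to −1 satisfies exclusion 1. If the 5.4 bar begins only with treatment, nothing stands in the way. If it begins at consent, this order still passes within the 28 days: routine-care scan, palliative radiation, consent, C1D1. The shrinkage then falls after baseline and before C3D1.

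**2. When does one irradiated lesion give a PR?** Let *w* be its share of baseline SPD and *s* its proportional shrinkage, with the other targets unchanged. The fall in SPD is *w* × *s*, and a PR needs *w* × *s* ≥ 0.50, so *w* ≥ 0.50 / *s*.

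| Shrinkage *s* | Minimum share *w* |
|---|---|
| 100% | 50.0% |
| 90% | 55.6% |
| 80% | 62.5% |
| 70% | 71.4% |
| 50% | 100% (sole target) |

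With *k* equal targets, complete loss of one gives a fall of 1/*k*: 100% for one, 50% for two (just a PR), 33.3% for three. With three or more equal targets, one irradiated lesion cannot produce a PR alone.

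**3. Worked example (invented sizes).** Target products are 12, 6 and 5 cm², so SPD = 23. The 12 cm² node is irradiated after the scan and falls to 1.5; the other two shrink by 10% to 5.4 and 4.5.

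- All targets: 1.5 + 5.4 + 4.5 = 11.4, and (23 − 11.4)/23 = 50.4%, a PR.
- Without the irradiated node: 11 to 9.9, a fall of 1.1/11 = 10%, stable disease.

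The node holds 12/23 = 52.2% of SPD and shrinks 10.5/12 = 87.5%. With the others unchanged the fall would be 10.5/23 = 45.7%, short of a PR, so this case is close to the line.

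**4. Effect on ORR.** One patient in 12 is 1/12 = 8.3 points. For example, 3/12 = 25.0% (exact 95% CI 5.5 to 57.2) becomes 4/12 = 33.3% (9.9 to 65.1).

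**5. Illustration only.** Suppose a share *q* of patients have a target irradiated after baseline, half of those who would not otherwise respond are scored as responders for that reason, and true ORR is 35%. The inflation is *q* × 0.5 × (1 − 0.35): 3.25 points at *q* = 10% and 6.5 points at *q* = 20%. None of these inputs describes this trial; the documents give no frequency.

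**Scope.** This arithmetic covers CT-based response in PTCL. SPD is used because Appendix C defines PR by it, although 8.1 also speaks of a sum of diameters. Appendix F gives no response threshold for mSWAT, so no figure can be derived for CTCL.

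**The case against.** The strongest reply is Protocol 5.4. If its bar runs from consent, radiation after a study scan taken under consent is already forbidden, and only the routine-care-scan route remains. That narrows the gap. It does not close it, because 6.7 expressly accepts routine scans and 5.4 gives no start. A reader might infer that radiation is barred only from C1D1 onward; the text does not say that either.

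The second reply is that a false PR needs a dominant lesion. This stands and limits the claim.

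Third, ORR is a secondary, preliminary measure, SAP 9.1 tests no formal hypothesis, and the intervals at n = 12 are wide. This lowers the stakes. But a wider interval does not correct a response credited to the wrong treatment.

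Several stronger readings are tempting and are not supported:

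- **That all pre-study radiation inflates ORR.** If it comes before the baseline scan, the lesion is measured already reduced, with perhaps less room to fall. No clear upward bias follows.
- **That the systemic washout has the same flaw.** It is shorter than the scan window, and Appendix B equates five Tenalisib half-lives with 48 hours. But inclusion 3 admits only relapsed or refractory disease, which gives little reason to expect delayed shrinkage from the failed therapy.
- **That false CRs follow readily.** Appendix C requires clearance at all sites, so one field suffices only if all remaining disease lies in it or the rest has cleared.
- **That CTCL is affected to the same degree.** mSWAT sums involvement over 12 body regions, so a limited field would usually move it little.

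**Conclusion.** The point holds in a limited form. Followed as written, the plan can credit the combination with a PR caused by palliative radiation given after the baseline scan and before C1D1. Three conditions must be met: the radiation follows the scan, the irradiated lesion is a target, and it carries enough of the SPD (at least 50% if it vanishes, 62.5% at 80% shrinkage, other targets unchanged). Each such patient adds 8.3 points to a 12-patient ORR. How many there would be cannot be told from the documents, so no overall bias can be stated; the 3 to 7 point illustration rests entirely on assumed inputs. The defect lies in a stated selection rule and not merely in missing detail, and it is worth correcting because the correction is cheap.

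**What to change.** - **Protocol 8.1.** Add: *A lesion irradiated before C1D1 is recorded as non-target and left out of the SPD, unless progression in that lesion is documented on an assessment made after the radiation.*
- **SAP 10.5.1.** Add an ORR sensitivity analysis that counts as a non-responder any patient, PTCL or CTCL, irradiated after the baseline scan or mSWAT, including patients whose only measurable lesion was irradiated. Report it beside the main ORR.
- **Protocol 5.4.** State when the bar on radiation begins.
- **Protocol 6.3, 6.4 and 6.7.** Reconcile the 28-day and 28-week scan windows.

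mSWAT scoring, inclusion criterion 6 and the use of palliative radiation stay as they are, and no repeat scan is required.

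The cost is a few lines of text and one extra table. Prior radiation is already recorded (Protocol 6.3.4), and listings of prior therapy, target lesions and mSWAT are planned (SAP 14). The site and date of radiation must be captured in enough detail to place it against the lesion and the baseline assessment; the documents do not show whether they are. The downside is that a few patients will have fewer target lesions, or none. The sensitivity analysis is deliberately strict and may count a genuine responder as a failure, so it should be read as a lower bound with respect to this problem.
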